12. ADVERSE EVENT REPORTING REQUIREMENTS

12.1 Adverse Event Definition

An adverse event (AE) is any unfavorable and unintended sign, symptom, or disease temporally associated with the use of an investigational medicinal product (IMP) or other protocol-imposed intervention, regardless of attribution.

This includes the following:

- AEs not previously observed in the patient that emerge during the protocol-specified AE reporting period, including signs or symptoms associated with NHL that were not present prior to the AE reporting period
- Complications that occur as a result of protocol-mandated interventions
- If applicable, AEs that occur prior to assignment of study treatment associated with medication washout, no treatment run-in, or other protocol-mandated intervention.
- Preexisting medical conditions (other than the condition being studied) judged by the investigator to have worsened in severity or frequency or changed in character during the protocol-specified AE reporting period

All subjects will be monitored for AEs during the study. Assessments may include monitoring of any or all of the following parameters: the subject's clinical symptoms, laboratory,

pathological, radiological or surgical findings, physical examination findings, or findings from other tests and/or procedures.

Adverse Event Reporting Period

All AEs will be reported until 30 days after the last dose of study treatment or the start of new anticancer therapy (whichever comes first).. AEs and serious adverse events (SAEs) will be recorded on the AE page of the CRF and in the subject's source documents. All SAEs must be reported to Celgene Drug Safety within 24 hours and AstraZeneca within 7 days of the Investigator's knowledge of the event by facsimile, or other appropriate method, using the SAE Report Form, or approved equivalent form.

12.1.1 Adverse Event Characteristics and Related Attributions

METHODS AND TIMING FOR ASSESSING AND RECORDING SAFETY VARIABLES

The investigator is responsible for ensuring that all AEs and SAEs that are observed or reported during the study are collected and reported to the FDA, appropriate IRB(s), and Sponsor-investigator/industry supporters in accordance with CFR 312.32 (IND Safety Reports).

Assessment of Severity of Adverse Events

- **CTCAE term (AE description) and grade:** The descriptions and grading scales found in the revised NCI Common Terminology Criteria for Adverse Events (CTCAE) version 4.0 will be utilized for AE reporting. A copy of the CTCAE version 4.0 can be downloaded from the CTEP web site (<http://ctep.cancer.gov>)

Adverse Event Severity Grading Scale for Events Not Specifically Listed in NCI CTCAE

Grade	Severity
1	Mild; asymptomatic or mild symptoms; clinical or diagnostic observations only; or intervention not indicated
2	Moderate; minimal, local, or non-invasive intervention indicated; or limiting age-appropriate instrumental activities of daily living ^a
3	Severe or medically significant, but not immediately life-threatening; hospitalization or prolongation of hospitalization indicated; disabling; or limiting self-care activities of daily living ^{b,c}
4	Life-threatening consequences or urgent intervention indicated ^d
5	Death related to adverse event ^d

NCI CTCAE = National Cancer Institute Common Terminology Criteria for Adverse Events.

Note: Based on the most recent version of NCI CTCAE (v5.0), which can be found at: http://ctep.cancer.gov/protocolDevelopment/electronic_applications/ctc.htm

- a. Instrumental activities of daily living refer to preparing meals, shopping for groceries or clothes, using the telephone, managing money, etc.
- b. Examples of self-care activities of daily living include bathing, dressing and undressing, feeding oneself, using the toilet, and taking medications, as performed by patients who are not bedridden.
- c. If an event is assessed as a "significant medical event," it must be reported as a serious adverse event
- d. Grade 4 and 5 events must be reported as serious adverse events

- **Attribution** of the AE:

- Definite – The AE *is clearly related* to the study treatment.
- Probable – The AE *is likely related* to the study treatment.
- Possible – The AE *may be related* to the study treatment.
- Unlikely – The AE *is doubtfully related* to the study treatment.
- Unrelated – The AE *is clearly NOT related* to the study treatment.

Expected adverse events are those adverse events that are listed or characterized in the Package Insert (P.I) or current Investigator Brochure (I.B).

Unexpected adverse events are those not listed in the P.I or current I.B or not identified. This includes adverse events for which the specificity or severity is not consistent with the description in the P.I. or I.B. For example, under this definition, hepatic necrosis would be unexpected if the P.I. or I.B. only referred to elevated hepatic enzymes or hepatitis.

For patients receiving combination therapy, causality will be assessed individually for each protocol-mandated therapy.

PROCEDURES FOR ELICITING, RECORDING, AND REPORTING ADVERSE EVENTS

Eliciting Adverse Events

A consistent methodology for eliciting AEs at all subject evaluation time points should be adopted. Examples of non-directive questions include:

- “How have you felt since your last clinical visit?”
- “Have you had any new or changed health problems since you were last here?”

12.1.2 Recording of Adverse Events

All adverse events will be recorded on a patient specific adverse event log. The AE log will be maintained by the research staff and kept in the patient’s research chart.

12.1.3 Reporting of AE to WCM IRB

The participating investigator will report all adverse events and serious adverse events to the Principal Investigator and to the IRB according to the local IRB’s policies and procedures in reporting adverse events. In the event of a multi-center study, the Principal Investigator will report adverse events and serious adverse events from all participating sites to the WCM IRB according to the IRB’s policies and procedures in reporting adverse events.

12.2 Definition of SAE

A serious adverse event (SAE) is any AE occurring at any dose that:

- Results in death;
- Is life-threatening (i.e., in the opinion of the Investigator, the subject is at immediate risk of death from the AE);
- Requires inpatient hospitalization or prolongation of existing hospitalization (hospitalization is defined as an inpatient admission, regardless of length of stay);
- Results in persistent or significant disability/incapacity (a substantial disruption of the subject’s ability to conduct normal life functions);
- Is a congenital anomaly/birth defect;
- Constitutes an important medical event

Important medical events are defined as those occurrences that may not be immediately life threatening or result in death, hospitalization, or disability, but may jeopardize the subject or require medical or surgical intervention to prevent one of the other outcomes listed above. Medical and scientific judgment should be exercised in deciding whether such an AE should be considered serious.

Adverse Events (AEs) for malignant tumours reported during a study should be assessed as Serious

AEs. If no other seriousness criteria apply, the 'Important Medical Event' criterion should be used. In certain situations, however, medical judgement on an individual event basis should be applied to clarify that the malignant tumour event should be assessed and reported as a Non-Serious AE. For example, if the tumour is included as medical history and progression occurs during the study, but the progression does not change treatment and/or prognosis of the malignant tumour, the AE may not fulfill the attributes for being assessed as Serious, although reporting of the progression of the malignant tumor as an AE is valid and should occur. Also, some types of malignant tumours, which do not spread remotely after a routine treatment that does not require hospitalization, may be assessed as Non-Serious; examples include Stage 1 basal cell carcinoma and Stage 1A1 cervical cancer removed via cone biopsy. SPM that occurred after 28 days from last dose, and was considered related to any of the study investigational products, will need to be reported and communicated to AZ/BMS/Genentech

Adverse Events of Special Interest (AESI) are events that may not typically be considered to meet the regulatory criteria for expedited reporting, but that for a specific protocol are being reported via expedited means in order to facilitate the timely review of safety data and narrative (may be requested by the FDA or the industry supporters). It can be e.g. a non-serious non-specific start of an event, which may be an early manifestation of a serious potential risk. The same SAE reporting form, assessment and reporting timelines apply to AESIs. For reporting purposes they need to be treated as if they were serious events even when these events are non-serious and do not meet seriousness criteria. The following events are adverse events of special interest (AESIs) for subjects exposed to acalabrutinib, and must be reported to the Sponsor-investigator and industry supporters expeditiously, irrespective of regulatory seriousness criteria or causality: Ventricular arrhythmias (e.g., ventricular extrasystoles, ventricular tachycardia, ventricular arrhythmia, ventricular fibrillation, etc.)

Events not considered to be SAEs are hospitalizations for:

- A standard procedure for protocol therapy administration. However, hospitalization or prolonged hospitalization for a complication of therapy administration will be reported as an SAE.
- Routine treatment or monitoring of the studied indication not associated with any deterioration in condition. The administration of blood or platelet transfusion as routine treatment of studied Indication. However, hospitalization or prolonged hospitalization for a complication of such transfusion remains a reportable SAE.
- A procedure for protocol/disease-related investigations (e.g., surgery, scans, endoscopy, sampling for laboratory tests, bone marrow sampling). However, hospitalization or prolonged hospitalization for a complication of such procedures remains a reportable SAE.
- Hospitalization or prolongation of hospitalization for technical, practical, or social reasons, in absence of an AE.
- A procedure that is planned (i.e., planned prior to starting of treatment on study); must be documented in the source document and the CRF. Hospitalization or prolonged hospitalization for a complication remains a reportable SAE.

- An elective treatment of or an elective procedure for a pre-existing condition unrelated to the studied indication.
- Emergency outpatient treatment or observation that does not result in admission, unless fulfilling other seriousness criteria above. If an AE is considered serious, both the AE page/screen of the CRF and the SAE Report Form must be completed.

The following event will NOT be considered SAE:

- Leukopenia and lymphopenia of any grade as these are expected pharmacodynamic outcomes of study treatment.
- Grade 3 or 4 neutropenia that is not accompanied by fever $\geq 100.4^{\circ}\text{F}$ [38°C]) and improves to Grade ≤ 2 by Day 1 of the next cycle
- Grade 3 thrombocytopenia that does not result in bleeding and improves to Grade ≤ 2 by Day 1 of the next cycle
- Grade 3 or 4 anemia
- Grade 3 nausea or vomiting ≤ 7 days (in the absence of premedication or that can be managed with oral or IV anti-emetics)

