SCHEMA – ALO FEASIBILITY COHORT

Note

- Treatment includes 12 cycles of induction followed by maintenance. Patients will receive therapy until disease progression, development of unacceptable toxicity, or voluntary withdrawal. Acalabrutinib and lenalidomide can be discontinued after 24 cycles of treatment for subjects achieving MRD-negative CR during maintenance.
- MRD will be measured in peripheral blood at the conclusion of 6 and 12 cycles of induction treatment. Additional MRD measurements in peripheral blood will be collected every 4 cycles during maintenance.
- Imaging studies: PET/CT is required at baseline and time to confirm CR.

STUDY PROCEDURES – ALR

Table 1. Schedule of ALR Study Procedures¹

Procedure	Screening	Treatment Phase							Therapy Discontinuation	Follow-up Phase	
		Cycle 1				Subsequent cycles	Every 3 cycles Year 1	Every 4 cycles Year 2	Every 6 cycles Year 3-5		
		Day 1	Day 8±1	Day 15±1	Day 22±1						
Staging											
Lymph node/tissue biopsy ²	X										
Bone marrow aspirate & biopsy ³	X						Time to confirm CR				
Staging CT scan (or MRI) ⁴	X						X	X	X	X	
PET/CT ⁴	X						Time to confirm CR				
MRD Assay ⁵	X						Cycles 6 & 12	X	Every 6 cycles		
Laboratory Studies											
CBC with differential	X	X	X	X	X	X ¹²				X	
CMP including LFT	X	X	X	X	X	X				X	
LDH, uric acid ¹⁴ , phosphate ¹⁴ , PT/INR ¹⁴ , aPTT ¹⁴	X	X	X	X	X	X				X	
Creatinine clearance ⁶	X										
Thyroid function test TSH, T4, T3 uptake	X						X	X	X	X	
HBsAg, HBsAb, HBcAb, HCV, HIV ⁷	X										
HBV DNA testing ⁷	X						X	X	X	X	
Pregnancy testing ⁸	X	X				X				X	
Buccal Swab / saliva sample ²	X										
Other Evaluations											
Physical examination / vital signs ¹³	X	X	X	X	X	X				X	
Height & weight	X	X				X				X	
ECOG performance status	X	X				X				X	
MIPI score	X										
12-lead ECG ⁹	X										
FACT-Lym QOL questionnaires	X						X	X	X	X	
Concomitant medications	X	X	X	X	X	X				X	
Register Revlimid REMS® program	X										
Prescribe via Revlimid REMS® ¹⁰		X				X					
Adverse events assessment		X	X	X	X	X	X	X	X		
Correlative studies ¹¹		X	X	X	X	X				X	
Obtain Follow-Up treatment										X	

Obtain Follow-Up survival										X
---------------------------	--	--	--	--	--	--	--	--	--	---

¹ Unless otherwise specified, all screening requirements are within 28 days, all other assessments and procedures are +/- 3 days.

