5.2.3 Treatment Discontinuation

At treatment discontinuation, subjects will undergo off study evaluations within 28 days of last dose.

- Physical examination with vital signs and performance status
- AE assessment
- CBC with differential
- Serum chemistries to include TFT, CMP, LDH, phosphate and uric acid
- Concomitant medications
- HBV viral DNA in HBcAb positive, asymptomatic carrier
- Correlative blood samples
- Pregnancy test (for females of childbearing potential)
- CT scan (or MRI) of neck/chest/abdomen/pelvis (and other areas if indicated to evaluate sites of disease involvement); PET scan at discretion of investigator
- FACT-Lym quality-of-life questionnaires
- Telemedicine/virtual visits will be allowed where physical exam and vital signs may not be collected.
- Follow-up contact every 6 months until death

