5.6 Duration of Follow Up

The Follow-up Period for each subject begins upon study treatment discontinuation. A treatment discontinuation safety visit occurs within 28 days of treatment discontinuation. Subjects will be followed for subsequent anti-lymphoma therapies and survival every 6 months according to the schedules described in Tables 1 and 2.

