The Rituxan AESI are: none

The Gazyva AESI are:

- All TLS (irrespective of seriousness, causality or severity)
- Second Malignancies

Other Special Situations Reports

The following other Special Situations Reports should be collected even in the absence of an Adverse Event and transmitted to Genentech:

- Data related to the Product usage during breastfeeding
- Data related to overdose, abuse, misuse or medication error (including potentially exposed or intercepted medication errors)
- In addition, reasonable attempts should be made to obtain and submit the age or age group of the patient, in order to be able to identify potential safety signals specific to a particular population

Product complaints

A Product Complaint is defined as any written or oral information received from a complainant that alleges deficiencies related to identity, quality, safety, strength, purity, reliability, durability, effectiveness, or performance of a product after it has been released and distributed to the commercial market or clinical trial.

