12.2.3 Reporting of SAE to AstraZeneca

Time period for collection of adverse events

AEs will be collected from time of signature of informed consent form throughout the treatment period and including 30 days after the last dose of study treatment. After the signing of the ICF and prior to the first dose of study treatment all SAEs, regardless of causality, must be reported. All AEs will be reported until 30 days after the last dose of study treatment or the start of new anticancer therapy (whichever comes first). After this period, investigators should report SAEs or other AEs of concern that are believed to be related to prior treatment with study treatment. All SAEs that occur during the reporting period should be followed to resolution or until the investigator assesses the subject as stable, or until the subject is lost to follow up or withdraws consent. Resolution/stable means the subject has returned to baseline state of health or the investigator does not expect any further improvement or worsening of the event.

All SAEs/AESIs will be recorded and reported to the Sponsor-investigator or designee within 24 hours. The investigator will submit any updated SAE/AESI data to the Sponsor-investigator within 24 hours of it being available. Investigators are not obligated to actively seek AE or SAE data in former study subjects. However, if at any time after a subject's last visit the investigator learns of any SAE, including a death, that is considered to be reasonably related to the study treatment or study participation, the investigator may notify the Sponsor-investigator.

Reporting of serious adverse events to AstraZeneca

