12.5 AE/SAE Follow Up

All SAEs and AEs reported during this study will be followed until resolution or until the investigator confirms that the AE/SAE has stabilized and no more follow-up is required. This

requirement indicates that follow-up may be required for some events after the patient discontinues participation from the study.

For studies involving collection of survival data the investigator after the end of the adverse event reporting period (defined as 28 days after the last dose of study drug) should report all deaths, (regardless of cause), and any serious adverse event including development of cancer or a congenital anomaly in a subsequently conceived offspring of a female subject including pregnancy occurring in the partner of a male study subject] who participated in the study that is believed to be related to prior exposure to study drug.

Case Transmission Verification will be performed by both parties during this period to ensure successful transmission of Single case reports.

Other Reports

The investigator will forward a copy of the Final Study Report to Genentech upon completion of the Study.

STUDY CLOSE-OUT

Any study report submitted to the FDA by the Sponsor-Investigator should be copied to Genentech. This includes all IND annual reports and the Clinical Study Report (final study report). Additionally, any literature articles that are a result of the study should be sent to Genentech. Copies of such reports should be mailed to the assigned Clinical Operations contact for the study:

[contact]

And to Genentech Drug Safety CTV oversight mail box at: [contact]

QUERIES

Queries related to the Study will be answered by the Investigator. However, responses to all safety queries from regulatory authorities, Ethics Committees and Institutional Review Board or for publications will be discussed and coordinated between the Parties. The Parties agree that Genentech shall have the final say and control over safety queries relating to the Product. The Investigator agrees that it shall not answer such queries from regulatory authorities and other sources relating to the Product independently but shall redirect such queries to Genentech.

Both Parties will use all reasonable effort to ensure that deadlines for responses to urgent requests from Regulatory Authorities and/or IRB/IEC for information or review of data are met. The Parties will clearly indicate on the request the reason for urgency and the date by which a response is required.

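### Late second cancers judged related are reportable, but no follow-up item asks about new cancers, so capture is passive and probably incomplete

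*Combined protocol and SAP*

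**What the plan says.** Reporting duties. Section 12.2 makes any "SPM that occurred after 28 days from last dose, and was considered related to any of the study investigational products" reportable to the three supporting companies, in mandatory terms. Section 12.5 says that once the adverse event period has ended investigators should report every death, and also "any serious adverse event including development of cancer" where it is believed related to prior exposure. Section 12.2.1 lists "Second Malignancies" as an event of special interest for obinutuzumab; the corresponding rituximab list is empty. Section 7.1.5 warns of second primary malignancies with acalabrutinib and asks that subjects be monitored for malignancy.

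Follow-up content. Section 5.6: "Subjects will be followed for subsequent anti-lymphoma therapies and survival every 6 months according to the schedules described in Tables 1 and 2". Section 5.2.3 adds "Follow-up contact every 6 months until death". The follow-up rows of Tables 1 and 2 are "Obtain Follow-Up treatment" and a matching row for survival. No row in either table names second malignancy.

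Later events. Section 12.2.3: "Investigators are not obligated to actively seek AE or SAE data in former study subjects". It then says that an investigator who learns of a related serious event after a subject's last visit may pass it on to the Sponsor-investigator. Earlier in the same section, related serious events and adverse events of concern after the window are ones that investigators should report.

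**The concern.** A reporting duty works only if some step brings the event to light. Neither follow-up item does so for a second cancer. Treatment for an unrelated new tumour is not anti-lymphoma therapy, and a cancer that has not caused death leaves survival status unchanged. A site could complete every scheduled contact correctly and never ask.

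Safety of ALR and of ALO are both secondary objectives (section 1.2), and section 11.3.3 tabulates adverse event frequency. With 28 patients planned for ALR and 10 for ALO, an unasked question can be the difference between reporting no second cancer and reporting one. Whether a case is known would also depend on which site heard of it, and the history may not be recoverable once a patient has died or been lost.

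**Working it through.** The plan states no second-cancer rate and no analysis target, so there is no figure to reproduce. The check sets the passages side by side.

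1. **What must be reported.** Section 12.2 covers late second cancers considered related. Because that section treats malignant tumours as serious events by default, most such cases would also fall under the post-window clauses of sections 12.2.3 and 12.5, both limited to events believed related. The obinutuzumab entry in section 12.2.1 carries no causality condition and no time limit; the plan does not say whether it extends beyond the window.

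2. **What is asked.** Sections 5.2.3 and 5.6 and the follow-up rows of Tables 1 and 2 give two items: later anti-lymphoma treatment, and survival. The intersection of steps 1 and 2 is empty: no scheduled item is directed at a new primary cancer.

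3. **What is sought beyond the schedule.** Section 12.2.3 releases investigators from seeking events in former subjects. It does not define that group, so it is unclear whether patients in six-monthly survival follow-up belong to it. The answer does not matter for step 2: if they are not former subjects, the schedule still contains no question for them.

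4. **What happens to an event that becomes known.** The wording differs in force: mandatory in section 12.2, recommended in section 12.5 and in one sentence of section 12.2.3, optional in a later sentence of section 12.2.3. One related cancer can fall under all three.

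5. **When the late rule begins.** Sections 12.2 and 12.5 use 28 days after the last dose. Sections 12.1 and 12.2.3 use 30 days, or the start of new anticancer therapy if sooner. On days 29 and 30 a second cancer can be both inside the general window (reported whatever the cause) and under the late rule (related cases only). If new therapy starts before day 28, the general window may close before the section 12.2 rule opens; the post-window clause in section 12.2.3 would still reach a related case.

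6. **Size.** For a given cohort, observed late cases = true late cases × c, where c is the proportion that sites come to know of and report. Since c cannot exceed 1, the error can only be downward. The documents give no value for c and no rate for the true number, so the range runs from none missed (c = 1) to all missed (c = 0), and nothing in the plan narrows it.

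**The case against.** The strongest reply is that the plan does not leave these events without a route. Related cancers that become known are reportable under sections 12.2, 12.2.3 and 12.5, all deaths are requested, and contact every six months until death gives a regular chance to hear of a diagnosis. A duty to report known related events is also logically compatible with having no duty to search. Second malignancy is not an endpoint, the special-interest listing applies only to the obinutuzumab cohort of 10, and the primary endpoint and stopping rules are untouched. All of this stands, and it keeps the point modest.

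It also rules out several stronger readings that a reader might infer:

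- That late second cancers would go wholly uncounted. The passive routes above contradict this.
- That every second cancer after day 28 must be reported. Section 12.2 covers only those considered related.
- That patients reaching 24 cycles then spend years in follow-up without being asked. Section 5.1 allows only acalabrutinib and lenalidomide to stop then, while the antibody continues. Section 5.2.2.1 keeps patients on rituximab alone on study visits, and section 5.6 starts follow-up only when study treatment ends. Second cancers on treatment are collected as adverse events.
- That second cancers mostly appear after treatment. Section 7.1.5 gives no timing.

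The reply does not answer the narrower point. Relatedness can be judged only for a cancer that someone has learned of, and no item is designed to elicit one.

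**Conclusion.** The point holds in limited form. After the reporting window, second primary cancers are ascertained passively and filtered by relatedness, so their count is probably incomplete and, if wrong, too low. The size of the shortfall cannot be estimated from the documents. The conclusion assumes that sites follow the written schedule and do not add questions of their own, and that no separate form or lab manual outside these documents collects new malignancies. It does not depend on how former subjects are defined. It affects long-term safety description for ALR and ALO only, and is worth correcting because the plan's own duties call for the information and the contact at which to ask already exists.

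**What to change.** - Add an item to the six-monthly contact in sections 5.2.3 and 5.6 and to the follow-up column of Tables 1 and 2: new primary malignancy since last contact, yes or no, with type, date and relatedness. Ask it regardless of suspected cause, so that relatedness is recorded as an attribute and does not act as a filter.
- In section 12.2.3, exempt this item from the sentence that removes the duty to seek later events, and state whether patients in survival follow-up count as former subjects.
- State in section 11.3 that second primary malignancies will be tabulated by cohort, separating those arising on treatment from those arising in follow-up.
- Reconcile the mandatory, recommended and optional reporting wording across sections 12.2, 12.2.3 and 12.5, and the 28-day window (12.2, 12.5) with the 30-day window (12.1, 12.2.3).

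The cost is one form field, a little site time at a contact that already takes place, and a text amendment. No visit, procedure or treatment rule changes.
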